3. Regular use of probiotics preparations in the 3 months prior to beginning the study treatment or use of any additional probiotics preparations (other than study treatment) at any time during the study period (including over the counter food supplements such as Activia, BioK, other oral or vaginal probiotics products (BUT not including other common forms of yogurt).
4. Chronic (daily) use of broad spectrum antibiotics.
5. History of infant with GBS sepsis.
6. IUGR, Fetal Anomalies-major diagnosed at time of second trimester anatomy ultrasound
7. Anticipated delivery <35 weeks for maternal/fetal indication
8. Placenta previa or accreta (with anticipated delivery prior to 35 weeks)

E. Outcomes:

1. **Primary:** GBS colonization at 35-37 weeks

2. Secondary: maternal ante- intra- and postpartum outcomes (urinary tract infections, chorioamnionitis, endometritis, cellulitis, bacteremia, sepsis, and other infectious morbidity) and neonatal outcomes (gestational age at delivery, APGAR scores, bilirubin levels, C-reactive protein, rule out sepsis evaluation, sepsis, pneumonia, meningitis, neonatal ICU admission, and length of hospital stay).

F. Agents:

1. Treatment arm: Study probiotic dietary supplement arm will consist of 1 capsule (>1 billion CFU/capsule) daily including two strains, Lactobacillus rhamnosus GR-1 and Lactobacillus reuteri RC-14, which have been shown to reduce the incidence of bacterial vaginosis and candidiasis. (43) Those two strains are present in Jarrow's Femdophilus, which is produced by Chr Hansen in Denmark under the brand name Urex. Shelf life is two years when stored at room temperature (max 25 degrees Celsius).

2. Control arm: Placebo arm will consist of one inert (heat inactivated) capsule daily.

G. Study Drug and Placebo Supply, Transport, and Storage:

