1. The baseline rectovaginal GBS colonization is approximately 25% in recent years in our practice, we have powered the study to identify a 40% reduction of GBS colonization to 15%. Using a two-tailed alpha of 0.05, 133 patients per arm (266 patients total) are needed to fulfill a power of 80% to detect a difference of 40% from current baseline GBS colonization of 25%.

2. Given anticipated 30% drop out/lost to follow-up and 10% preterm delivery prior to 35-37 weeks' gestation, we propose increasing our sample size by 40% to account for this subject loss. Therefore, we propose recruitment of 372 patients total (186 in each arm).

H. Statistics:

1. Analysis will be by intention to treat. Demographic data, specific information regarding the course of labor, and outcome variables will be collected on printed and numbered data sheets and entered into a relational database (Access; Microsoft Corporation, Redmond, WA). All data management and analysis will be performed using STATA version 7 software (StataCorp – College Station, TX). Descriptive statistics will be performed. All tests of significance will be 2-tailed and an alpha level of 0.05 will be used. Categorical data will be analyzed by the uncorrected χ^2 and Fisher exact test, as appropriate. Continuous data will be analyzed by the unpaired Student *t* test.

I. Data safety and monitoring plans:

1. The Protocol Director (PD) will be responsible for monitoring data collected.

2. Patient questionnaire/database assessing adverse events will be completed at each study visits, approximately every month. The questionnaire will assess adverse events, including rash, significant nausea/vomiting, significant diarrhea, persistent fevers. The questionnaire/database will also remind patients that such events must be reported to the Protocol Director immediately at all times.

3. Serious adverse events will be reported to the PD within one week. An interim analysis will be conducted to when primary outcome data is available for 150 subjects.

4. Data or events captured by the monitoring plan will be assessed monthly.

5. The following will be monitored:

- a. Side effects related to consumption of the probiotic or placebo capsules
- b. Rates of compliance

- c. GBS colonization culture results
- d. Neonatal morbidity or mortality, including but not limited to infection and duration of hospitalization

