Oral Probiotic Supplementation and Group B Streptococcus Rectovaginal Colonization in Pregnant Women: a Randomized Double-blind Placebo-controlled Trial

NCT01479478

July 14, 2017

[name], Principal Investigator
Stanford University
Stanford, California 94305

Statistical analysis plan

Treatment group characteristics will be summarized and reported using numbers and percentages for categorical data, means and standard deviation for normally distributed data, and medians and interquartile ranges (IQR) for non-normally distributed data. Characteristics will be compared between the treatment groups using the standardized mean difference.

Binary study outcomes will be compared between treatment groups using the Cochran-Mantel-Haenszel test. Normally distributed outcomes will be compared using linear regression adjusting for site. Non-normally distributed outcomes will be compared using the van Elteren (vE) test; a stratified Wilcoxon-Mann-Whitney test. In all cases treatment effects, 95% confidence intervals and p-values will be reported. All analyses will be performed according to intention-to-treat. P-values $\leq .05$ will be considered significant. All statistical analysis was performed using SAS 9.4.

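### The 0.05 significance rule covers about 17 secondary outcomes with no multiplicity control or exploratory label, so a chance 'significant' maternal or neonatal finding is likely enough to matter.

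*Protocol*

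**What the plan says.** Protocol section E (Outcomes) names one primary outcome, "GBS colonization at 35-37 weeks". The secondary outcomes follow in two lists:

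- Maternal, 7 items: "urinary tract infections, chorioamnionitis, endometritis, cellulitis, bacteremia, sepsis, and other infectious morbidity".
- Neonatal, 10 items: "gestational age at delivery, APGAR scores, bilirubin levels, C-reactive protein, rule out sepsis evaluation, sepsis, pneumonia, meningitis, neonatal ICU admission, and length of hospital stay".

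Protocol section H (Statistics) sets a single rule: "All tests of significance will be 2-tailed and an alpha level of 0.05 will be used". The SAP states: "In all cases treatment effects, 95% confidence intervals and p-values will be reported". It adds that p-values at or below .05 "will be considered significant". The SAP text does not mention primary or secondary outcomes at all.

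Neither document contains a multiplicity adjustment, a testing order, a ranking within the secondary list, or a statement that these outcomes are exploratory.

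**The concern.** The protocol separates primary from secondary outcomes when it lists them, but the significance rule ignores that separation. About 17 secondary comparisons may each be declared significant at 0.05, with nothing to limit or qualify the declarations.

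This matters because comparing perinatal infectious outcomes is the second of the trial's two specific aims, so these results will be read as findings. With an inert product, the rule would still quite often produce a declared effect on some maternal infection or neonatal outcome. The error runs both ways: it may appear as a benefit or as a harm of a supplement taken in pregnancy. Such a result could then be reported beside a null primary result with the word 'significant' attached and the plan's own text as authority.

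**Working it through.** The documents state no familywise error figure, so there is none to reproduce.

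**Inputs from the documents.** Secondary outcomes: 7 + 10 = 17 (Protocol E). Threshold: 0.05, two-sided (Protocol H, Statistics; the SAP has the same threshold). Binary tests: uncorrected chi-square or Fisher (Protocol), Cochran-Mantel-Haenszel, CMH (SAP). Arm sizes for the calculation: 133 evaluable and 186 recruited per arm (Protocol, Sample size calculation). They serve here only as plausible sizes; whether 133 is adequate is a separate question.

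**Inputs that must be assumed.** Event rates of the secondary outcomes and the correlations between them.

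**Step 1: independent tests, each at exactly 5%.** P(at least one) = 1 - 0.95^k.

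- k = 7 (maternal): 1 - 0.698 = 30%
- k = 10 (neonatal): 1 - 0.599 = 40%
- k = 17: 1 - 0.418 = 58%
- Expected false positives for 17 tests: 17 x 0.05 = 0.85

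**Step 2: rare binary outcomes.** Twelve of the 17 items are binary, and several are rare. A test on very few events cannot use its full 5%. Exact sizes at 133 per arm, taking chi-square where expected counts reach 5 and Fisher otherwise, against an unstratified CMH-type test:

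| Assumed event rate | Chi-square/Fisher | CMH-type |
|---|---|---|
| 0.2% | 0.0000 | 0.0002 |
| 0.5% | 0.0001 | 0.0048 |
| 1% | 0.0013 | 0.0241 |
| 2% | 0.0100 | 0.0452 |
| 3% | 0.0229 | 0.0437 |
| 5% | 0.0449 | 0.0475 |
| 10% | 0.0507 | 0.0474 |

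Worked case with middling assumed rates: two outcomes at 5%, two at 10%, one each at 3%, 2% and 1%, two at 0.5%, two at 0.2% and one at 0.1% (size 0.0000 by either test). The five continuous or ordinal neonatal outcomes are taken at 0.05 each.

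- Chi-square/Fisher: 1 - 0.9551^2 x 0.9493^2 x 0.9771 x 0.9900 x 0.9987 x 0.9999^2 x 0.95^5 = 1 - 0.614 = 39%
- CMH-type: 1 - 0.9525^2 x 0.9526^2 x 0.9563 x 0.9548 x 0.9759 x 0.9952^2 x 0.9998^2 x 0.95^5 = 1 - 0.562 = 44%

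Across low to high assumed rates (0.1% to 15%) and 133 to 186 per arm, still independent, the chance is 33-45% with chi-square/Fisher and 41-54% with the CMH-type test.

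**Step 3: correlation alone.** For 17 full-size tests with a common correlation between test statistics, simulation gives 57% at 0.1, 49% at 0.3, 39% at 0.5 and 27% at 0.7.

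**Step 4: both together.** Null simulations in which each woman's outcomes share a latent correlation of 0 to 0.7:

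| Assumed rates | Per arm | Chi-square/Fisher | CMH-type |
|---|---|---|---|
| 0.2-12% | 133-186 | 30-43% | 36-51% |
| 0.2-15% | 117-167 | 27-45% | 34-53% |

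The sizes 117 and 167 are about half of 372 x 0.7 x 0.9 = 234 and 372 x 0.9 = 335. A site-stratified simulation of 16 outcomes with the SAP's CMH and van Elteren tests, rates 0.2-10% and 234-335 women, gave 41-47%, with 0.5-0.6 false positives per trial.

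These results centre on roughly 30-50%, with the protocol's tests at the lower end and the SAP's at the upper.

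**The case against.** The best case for leaving the plan alone has four parts.

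1. *The hierarchy exists.* The protocol labels one outcome primary. It is the only one in the stated hypothesis and the only one powered. A reader might infer that the plan gives each secondary test the same evidential standing as the primary, or that the secondary tests inflate the primary's error rate. The documents support neither. The labels are there, and the primary is tested alone at 0.05 whatever the secondary results show. This part stands, and it limits the point to how secondary results are declared.

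2. *The error figure is softer than it looks.* A reader might take 40-58% as the chance itself. But 58% requires 17 independent tests each at full size, and 40% is the same formula for the neonatal list alone, so it is not a floor. Rare events pull the chance down. So does overlap, for example between sepsis work-up, admission to intensive care and length of stay. This stands too. In the other direction, the maternal list ends in an open category and Apgar scores are plural, so the number of tests could exceed 17.

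3. *Unadjusted secondary outcomes are common practice, and the SAP already reports effects with confidence intervals.* True, and it makes the remedy small. But reporting unadjusted p-values is different from declaring each one significant at 0.05, and these documents do the latter.

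4. *Stricter labelling could blunt detection of harm.* Maternal and neonatal morbidity are also monitored for safety (Protocol, Data safety and monitoring plans). This is a fair caution, and the replacement wording must exempt that monitoring.

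**Conclusion.** The point holds as a defect in the decision rule for secondary outcomes. About 17 of them can be declared significant at 0.05 with no control and no exploratory label. With an ineffective product, the chance of at least one such declaration is roughly 30-50%. That range rests on assumed event rates of about 0.1% to 15% and correlations from 0 to 0.7, since the documents give neither; strong overlap combined with Fisher tests can take it slightly below 30%. The 58% figure is a benchmark for 17 independent full-size tests and should not be quoted as the trial's error rate.

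The secondary tests do not alter the type I error of the primary comparison, and nothing here casts doubt on that result. Nor do the documents show that a formal correction is required, because they attach no success claim to any secondary outcome. What cannot be read reliably under the present rule is a 'significant' finding under Aim 2.

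**What to change.** Replace the significance sentence in Protocol section H (Statistics) and in the SAP with the same text:

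> All tests are two-sided. Only GBS colonization at 35-37 weeks is declared significant at 0.05. Secondary outcomes are reported as effects with 95% CIs and unadjusted two-sided p-values, are labelled exploratory, and are not called significant. Safety monitoring of maternal and neonatal morbidity is not restricted by this rule.

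This keeps the protocol's two-sided rule for every test and states it in the SAP, which is silent on it. No data collection, sample size or test changes. The cost is that a nominal p of 0.03 on a secondary outcome can no longer be called significant.

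A Holm correction within the maternal and neonatal lists is not recommended. The open maternal category and plural Apgar scores leave the family sizes unfixed, and two families each held at 5% would still allow about 1 - 0.95^2 = 10% across both if the families were independent.

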Appendix B: Patient Questionnaire to be completed at monthly study visits.

Oral Probiotic Supplementation and Group B Streptococcus Rectovaginal Colonization in Pregnant Women: a Randomized Double-blind Placebo-controlled Trial

NCT01479478

July 14, 2017

[name], Principal Investigator
Stanford University
Stanford, California 94305

Statistical analysis plan

Treatment group characteristics will be summarized and reported using numbers and percentages for categorical data, means and standard deviation for normally distributed data, and medians and interquartile ranges (IQR) for non-normally distributed data. Characteristics will be compared between the treatment groups using the standardized mean difference.

Binary study outcomes will be compared between treatment groups using the Cochran-Mantel-Haenszel test. Normally distributed outcomes will be compared using linear regression adjusting for site. Non-normally distributed outcomes will be compared using the van Elteren (vE) test; a stratified Wilcoxon-Mann-Whitney test. In all cases treatment effects, 95% confidence intervals and p-values will be reported. All analyses will be performed according to intention-to-treat. P-values $\leq .05$ will be considered significant. All statistical analysis was performed using SAS 9.4.
